#### **Inclusion criteria:**

1. Subjects must be between the ages of 18 and 75 years old;
2. Both males and females will be included.
3. Be able and willing to provide signed informed consent and follow study instructions

#### **Exclusion criteria:**

1. Subjects will be excluded if they present with any systemic or ocular conditions that in the opinion of the Principal Investigator may prevent them from completing the tests.

### **Scheduled Visits**

Patients will be assessed at baseline, 3 months and 6 months (final visit).

### **Unscheduled visits**

## **Study Title: Macular Pigment and Visual Performance in Glaucoma Patients**

**IRB Protocol: 00093041  
NCT03959592**

**PI: [name], Ph.D**

An unscheduled visit may be any visit to the Investigator other than the specific visits requested in the protocol as possibly required for the subject's ophthalmic condition. The Investigator will perform all procedures necessary to evaluate the study participant at these visits and record any adverse events in the source document.

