#### **General evaluation:**

The following is a list of assessments to be conducted at each patient visit.

1. Measurement of MPOD. Equipment: The Heidelberg Spectralis with MPOD module will be used to obtain an MPOD spatial density profile; no dilation required. Patient time: 15 minutes.

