**PI: [name], Ph.D**

2. CS testing. Equipment: M&S Technologies Smart System. Sine-wave gratings with frequencies of 1.5, 3, 6, 12, and 18 cycles / degree will be used to generate a contrast sensitivity function. Patient time: 15 minutes.
3. DG testing. Equipment: M&S Technologies Smart System with integrated glare testing system. Glare testing will be similar to the CS test, but only 6 cycles / degree will be assessed. Patient time: 10 minutes.
4. DA assessment. Equipment: MacuLogix Adapt Dx. Patients' speed of rod-mediated dark adaptation will be measured at 12o retinal eccentricity. This technology allows for rapid (< 10 minutes) assessment. Patient time: 10 minutes.
5. Visual Function Questionnaire (NEI VFQ-25). Patient time: 10 minutes.
6. Point-spread function; optical quality of the eye. Equipment: HD Analyzer. Patient time: 1 minute.
7. Visual field assessment. Equipment: SAP 24-2; SAP 10-2. Patient time (total): 15 minutes.
8. Review of medical history;

The results of the above assessments will be convolved with patients' clinical exam data to form the study's comprehensive database.

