#### **Unknown/unforeseeable risks**

In addition to the risks and discomforts listed here, there may be other risks that are currently not known. Subjects will be informed if any other potential risk becomes known through the duration of the study. Also, the risks and discomforts may occur more often or be more severe than have been seen before and written in this form.

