### **Data & Safety Monitoring**

In accordance with federal regulations the PI will monitor for, review, and promptly report to the IRB, appropriate institutional officials, and the appropriate regulatory agency head all unanticipated problems involving risks to subjects or others that occur in the course of a subject's participation in a research study (45 CFR 46.103(b)(5)(i) and 21 CFR 56.108(b)(1)), and all reportable adverse events (AEs) will be submitted per the DUHS IRB policies.

All examinations will be performed by appropriately trained personnel. If any incidental findings are discovered during testing, the patient will be verbally informed and referred to a physician of the appropriate specialty, and eligibility to the study will be reassessed.

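### Adverse-event recording is spelled out only for unscheduled visits; no routine enquiry is specified at the scheduled visits, so harms may be under-recorded and not fairly compared between arms

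*Combined protocol and SAP*

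**What the plan says.** Four places in the combined protocol and SAP bear on this.

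- **Unscheduled visits.** At these visits the investigator evaluates the participant as needed and must "record any adverse events in the source document". No other section gives an explicit instruction to record adverse events.
- **General evaluation.** The list is introduced with "The following is a list of assessments to be conducted at each patient visit". It holds seven tests and questionnaires and, as item 8, "Review of medical history", with no content or time stated. Scheduled Visits sets the times (baseline, 3 months, 6 months) and adds no further procedure.
- **Data & Safety Monitoring.** For unanticipated problems involving risk, "the PI will monitor for, review, and promptly report to the IRB" and other bodies. In addition, "all reportable adverse events (AEs) will be submitted per the DUHS IRB policies". Incidental findings during testing lead to informing and referring the patient and to a fresh look at eligibility.
- **Unknown/unforeseeable risks.** "Subjects will be informed if any other potential risk becomes known through the duration of the study".

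Data Analysis & Statistical Considerations describes no summary of adverse events by arm.

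**The concern.** The trial is a randomised, masked comparison with placebo, so it could yield an unbiased comparison of harms at almost no cost. That requires every patient to be asked the same question at the same times. The plan does not specify this.

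The instruction that does exist attaches to visits outside the schedule, which the text links, in awkward wording, to the ophthalmic condition. The product is taken by mouth, and a non-ocular complaint is the kind of event least likely to bring a patient back to an eye clinic.

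Two things are at stake. The undertaking to tell patients about newly known risks depends on the trial noticing them. And a low event count at the end could not be read as reassurance, because nobody could say what share of events had been captured.

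**Working it through.** **1. The text, side by side.**

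| Section | When it applies | Patients asked about events? | Non-reportable events recorded? |
|---|---|---|---|
| Unscheduled visits | Extra visits | Not stated | Yes |
| General evaluation, item 8 | Every visit | Possibly; content undefined | Not stated |
| Data & Safety Monitoring | Throughout participation | Not stated | Not stated; covers unanticipated problems and reportable events |
| Data Analysis | Final analysis | – | No table by arm described |

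No row provides a standard enquiry at 3 and 6 months with all events recorded.

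**2. What incomplete capture could do.** The plan has no adverse-event figure to reproduce. The one input from the documents is 30 patients per arm (Selection of Subjects). The true per-patient risk p and the share of events captured c are assumptions. The chance of recording at least one event in an arm is 1 − (1 − p·c)^30.

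| True risk p | c = 100% | c = 50% | c = 20% |
|---|---|---|---|
| 10% | 1 − 0.90^30 = 96% | 1 − 0.95^30 = 79% | 1 − 0.98^30 = 45% |
| 5% | 1 − 0.95^30 = 79% | 1 − 0.975^30 = 53% | 1 − 0.99^30 = 26% |

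**3. Reading a zero count.** With full capture, no events in 30 patients gives a one-sided 95% upper bound of 1 − 0.05^(1/30) = 9.5% on the risk. With partial capture that bound applies to p·c, so the bound on p is 9.5%/0.5 = 19% at half capture and 9.5%/0.2 = 47.5% at one-fifth.

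**4. The comparison between arms.** If capture is the same in both arms, the observed risk difference shrinks by the factor c. Risks of 10% and 5% differ by 5 points; at c = 20% the expected observed difference is 0.2 × 5 = 1 point. If the supplement causes a type of event that seldom prompts an eye visit, capture differs between arms and the comparison is also biased.

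**5. Room in the visit.** The timed items sum to 15 + 15 + 10 + 10 + 10 + 1 + 15 = 76 minutes of the 90 given in Subject Recruitment and Compensation. Item 8 has no time, so the 14-minute remainder is not all free.

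**The case against.** The strongest reply is that silence is not restriction. The unscheduled-visit text says what happens at those visits; it does not forbid recording elsewhere. The safety-monitoring section applies throughout participation, and submitting reportable events presupposes some means of noticing them. A history review at each visit is a natural point for new symptoms to surface. This stands as far as it goes. A reader might infer that adverse events are recorded only at unscheduled visits and that all others are lost; the documents do not support that reading.

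The reply does not close the gap. The monitoring section is a reporting duty for a subset of events and does not say that patients are asked, or that ordinary events are written down. The history review has no stated content, and nothing directs that what it reveals be recorded as an adverse event.

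It is also fair to say that safety is not among the stated purposes, that the Risks section describes the product as an over-the-counter supplement and study risks as low, and that no efficacy analysis is affected. These points limit the weight of the concern. They do not remove it: the protocol itself allows that unknown risks may exist and undertakes to report them to patients.

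Finally, the illustrative figures depend entirely on assumed rates. That is correct, which is why a range is shown.

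**Conclusion.** The concern holds in a limited form. Explicit recording of adverse events is specified only for unscheduled visits, no defined enquiry exists at the scheduled ones, and no comparison by arm is planned. Non-reportable harms, particularly non-ocular ones, may therefore be under-recorded, with capture depending partly on who seeks an extra visit. As written, the plan gives no sound basis for comparing supplement with placebo on harms.

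The size cannot be established from the documents. If capture lay between 20% and 100%, the chance of seeing at least one event of 10% risk among 30 patients would lie between 45% and 96%, and of 5% risk between 26% and 79%. These figures assume independent patients, all 30 followed, and capture unrelated to risk; attrition would lower them. They show how much could be lost, not that it will be. This is a worthwhile and inexpensive correction, not a threat to the efficacy conclusions.

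**What to change.** Add to the General evaluation list a standard open adverse-event question at the 3-month and final visits, worded identically for all patients, asked by staff masked to allocation and recorded in the source document. State what counts as an adverse event and how item 8 relates to the question. Add to Data Analysis & Statistical Considerations a table of all recorded events by arm, showing patients with at least one event and event counts, for the final report. Study Design & Procedures describes a one-year intervention while Scheduled Visits ends at 6 months; these sections need reconciling, and the question should be attached to every follow-up visit in the reconciled schedule.

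The cost is a few minutes per visit, one line in the visit list and one table. Sample size and alpha do not change.

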### **Subject Recruitment and Compensation**

Subject recruitment will be done at the Duke University Eye Center clinics. The study will also utilize D.E.D.U.C.E (Duke Enterprise Data Unified Content Explorer) an on-line research tool providing Duke investigators with access to clinical information collected as a by-product of patient care. The study will apply for a waiver of consent to identify potential subjects for the study. The PI will introduce potential eligible subjects to the study during their visit to the eye clinics, and if they are determined eligible a delegated key personnel will obtain consent from the subject. If the subject is not available for immediate consenting the PI will obtain the patient's permission to be contacted by telephone at a later date. A telephone script will then be used for the conversation. In addition, once the subject has the consent signed we will request access to their medical records through a medical records release form to obtain the participant's general medical history, previous use of systemic medications, previous use of ophthalmological medications, previous ocular examinations, previous ocular procedures, and results of other medical tests.

There will be no additional costs as a result of being in this study. Both macular carotenoid supplement and placebo will be provided by the manufacturer (MacuHealth LP, Birmingham, MI). Patients should be able to complete each visit within 90 minutes, and will be compensated a total of \$100 for study completion. This compensation is for expenses related to subject participation (parking, gas, and time) and will be provided by funding from the Department of Ophthalmology.

### **Consent Process**

We will use protected health information to screen for possible/eligible subjects. No PHI will leave Duke. A member of the eye care team will approach the potential participant to introduce the study. Knowledgeable key personnel will explain the study to the potential subjects and the Principal Investigator will be available during the consenting process to answer any questions the potential subjects may have about the study. The consenting process will occur in a private room and no study related activities will begin until the subject's consent is obtained. Only delegated key personnel can consent potential subjects.

A waiver of consent and HIPAA authorization will be filed with the Duke IRB to allow us to review PHI and health information to screen potential participants.

A telephone script will be submitted to schedule potential subjects in Maestro Care for study screening prior to full consent, and in case subjects are interested in participating and they cannot discuss the study in person when they are initially seen, after the PI introduces the study and key personnel to them.

### **Subject's Capacity to Give Legally Effective Consent**

Adult subjects able and willing to participate will sign the consent forms. If the vision of the potential subject is severely impaired enough to affect reading the consent document, the person obtaining consent, a study team member or a witness will read aloud and a witness will be required to sign the consent.

**PI: [name], Ph.D**

### **Risk/Benefit Assessment**

#### **Risks**

Risks from participating in the study are low. The primary risks for all participants are some discomforts, which are similar to those encountered in any complete eye examination. Participants will undergo non-invasive procedures used for diagnostic purposes. All medical instruments are FDA approved. The software for OCT Angiography and Macular pigment optical density analysis are currently undergoing FDA review and are not currently approved.

Lutein, zeaxanthin, mesozeaxanthin are over-the-counter nutritional supplements from natural sources. Lutein, zeaxanthin, mesozeaxanthin are likely safe when taken by mouth appropriately. There are no known risks or drug interactions associated with macular carotenoids as part of the diet. They are likely safe when used in the amounts found in food for pregnancy and breast-feeding

There is, however, the potential risk of loss of confidentiality. Every effort will be made to keep the information confidential; however, this cannot be guaranteed. Some of the questions that will be asked as part of this study may make the patients feel uncomfortable. Patient may stop their participation in this study at any time.

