L and Z are diet-derived, yellow-orange colored carotenoids obtained primarily from leafy-green vegetables (Sommerburg et al., 1998). L and Z are not synthesized by the body, and therefore must be obtained via dietary means; those who have diets rich in leafy greens, or supplement with sufficient L and Z tend to maintain and accumulate higher blood and tissue concentrations (Ciulla et al., 2001; Bone et al., 2003). One of the conspicuous features of L and Z is their specific accumulation in the macular retina (Snodderly et al., 1984b), where they can reach extremely high concentrations – values as high as 1.50 log optical density near the foveal center are not uncommon (e.g., Hammond et al. 1997); it is also not uncommon to see concentrations in the fovea that exceed 10,000 times that seen in the blood (Bone et al. 1993). Once deposited in the retina, some of the L is converted to a stereoisomeric form of zeaxanthin, called mesozeaxanthin (MZ; Neuringer et al. 2004). Although rare, MZ has been shown to exist in nature, and indeed in the human food chain - its presence has been recently verified in salmon, trout, and sardine skin, and also trout flesh (Nolan et al., 2014). Importantly, MZ has been shown to be readily deposited in the retina when taken in supplement form (Loughman et al., 2012). The accumulation of these three carotenoids in the macula yields a yellowish-orange coloration, classically known to ophthalmologists as the “macula lutea” (“yellow spot”; first noted by Buzzi, 1782). Today, this collective pigmentation is commonly referred to as macular pigment (MP; Wald, 1945), with concentrations typically expressed in terms of optical density (MPOD). Xanthophyll carotenoids such as L, Z, and MZ are especially potent antioxidants (Krinsky et al., 2003). Via a process called triplet excitation transfer (Ruban et al., 2002), L, Z, and MZ can regenerate to repeatedly “quench”

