### **Selection of Subjects**

All participants must have signed the consent form. A power analysis based on previous retinal response and corresponding visual performance data from AMD patients revealed that 30 patients each in both placebo and treatment groups would be required to detect effects, if present. Assuming some attrition, we plan to recruit a total of 60 patients, half of which would be randomly assigned to receive a macular carotenoid supplement, containing 10 mg L, 2 mg Z, and 10 mg MZ (to be consumed once daily with a meal). In terms of macular carotenoid content, 22 mg total is roughly equivalent to 2 large bowls of spinach. The other half would receive an identical pill, containing only sunflower oil (as with the active supplement, patients would be instructed to take one pill daily, with a meal). Baseline measures (see below) for patients consenting to enroll in the study would be determined shortly after enrollment, prior to the onset of supplementation.

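### Women from age 18 can enter with no pregnancy or breast-feeding criterion, but the protocol's only safety statement for that group is limited to food amounts, and the supplement is not shown to meet that limit

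*Combined protocol and SAP*

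**What the plan says.** **Who may enter.** Inclusion criteria: "Subjects must be between the ages of 18 and 75 years old" and "Both males and females will be included". The remaining inclusion item concerns consent and following instructions. The only exclusion reads "Subjects will be excluded if they present with any systemic or ocular conditions that in the opinion of the Principal Investigator may prevent them" and goes on to refer to finishing the study tests. Neither list mentions pregnancy or breast-feeding.

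**What they may receive.** Under Selection of Subjects, half of the 60 patients are randomised to "a macular carotenoid supplement, containing 10 mg L, 2 mg Z, and 10 mg MZ", one pill a day. The same section adds: "In terms of macular carotenoid content, 22 mg total is roughly equivalent to 2 large bowls of spinach".

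**What is said about safety.** The Risks text makes three relevant statements:
- The three carotenoids, MZ included, are judged probably safe with proper oral use. This sentence is general and does not mention pregnancy.
- No risks or drug interactions are known for dietary intake.
- For pregnancy and breast-feeding: "They are likely safe when used in the amounts found in food for pregnancy and breast-feeding".

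**What is said about food sources.** Background & Significance names leafy greens as the main source of L and Z. Of MZ it says "Although rare, MZ has been shown to exist in nature", then adds that it occurs in the human food chain and cites the skin of salmon, trout and sardines, and trout flesh.

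**The concern.** The authors considered pregnant and breast-feeding women and gave them a narrower assurance than everyone else, tied to food quantities. The eligibility lists do not carry that limit forward, and the intervention is a concentrated daily supplement. A pregnant or breast-feeding patient who meets the criteria could be randomised and take the active product throughout the treatment period, although the statement that covers her is not shown to describe what she takes. The IRB would be weighing risk on the same statement. At stake is participant protection and the coherence of the risk assessment, not the validity of any comparison between groups.

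**Working it through.** **Step 1. Reproduce the stated total.** Inputs from Selection of Subjects: L = 10 mg, Z = 2 mg, MZ = 10 mg.

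Total = 10 + 2 + 10 = 22 mg, which matches the protocol.

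**Step 2. Composition.**

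- MZ share = 10/22 = 45.5%
- L + Z share = 12/22 = 54.5%

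**Step 3. Does any exclusion reach this group?** The exclusion turns on whether a condition stops the patient completing the tests. The visit consists of imaging, contrast, glare, dark-adaptation and visual-field tests, a questionnaire and a history. Pregnancy and breast-feeding do not ordinarily prevent these, so investigator discretion as written does not close the gap.

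**Step 4. Which safety sentence applies?** The general sentence is not limited to food amounts, but it does not name this group. The sentence that does name it is limited to food amounts. If the general sentence were read as covering pregnancy at supplement amounts, the narrower one would serve no purpose.

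**Step 5. Is the supplement shown to be a food amount?**

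| Component | Daily amount | Food source named in the protocol | Does the spinach comparison support it? |
|---|---|---|---|
| L + Z | 12 mg | Leafy greens | Same source, but the comparison is stated for 22 mg, not 12 mg |
| MZ | 10 mg | Fish skin, trout flesh | No: not attributed to leafy greens, and no food quantity given |

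The comparison sets a total quantity beside a total quantity. It does not say that spinach contains MZ, so it cannot place 10 mg of MZ within the limit in the Risks text.

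**Step 6. What the comparison becomes if confined to L and Z.** The protocol's ratio is 22 mg to 2 bowls, or 11 mg per bowl. For L + Z: 12/11 = 1.09, about 1.1 bowls. Leaving two bowls beside 12 mg would introduce a new error.

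**Step 7. How many patients.** The documents give no age or sex distribution. If 0 to 2 of 60 were pregnant or breast-feeding, equal allocation would put about 0 to 1 on active product. Both ranges are assumptions.

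How far 10 mg of MZ departs from dietary intake cannot be calculated, because the protocol reports no MZ quantity for any food.

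**The case against.** The best case for the plan is as follows. The Risks text calls these over-the-counter supplements and gives a general oral-safety judgement that includes MZ. The background says MZ is part of the human food chain. Selection of Subjects does try to relate the amount to food. Very few glaucoma patients would be pregnant or breast-feeding, and no endpoint, test or sample-size result depends on the point. The section on unknown risks also warns that further risks may exist.

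Much of this stands and sets the limits of the point:

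- A reader might infer that all of the protocol's safety text is confined to food amounts. It is not; the general sentence has no such limit. Only the pregnancy and breast-feeding sentence carries it, and the dietary limit in the no-known-risks sentence is a separate matter.
- A reader might infer from the word rare, or from the 45% share, that the MZ content is excessive or harmful. The documents show neither. The 45% describes composition; it does not measure risk or excess over diet.
- A reader might infer that participants are misinformed at consent. The consent pages are not in the text available for this review, so nothing can be said about them.
- A reader might call this a direct contradiction. It is better described as an incomplete justification: the entry rule is wider than the stated safety basis is shown to be.

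What does not stand is the suggestion that these passages close the gap. None of them addresses pregnancy or breast-feeding at supplement amounts, and the general warning about unknown risks does not mention that group.

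**Conclusion.** The point holds in a narrow form. The eligibility lists admit pregnant and breast-feeding women by silence. The only statement about their safety is conditional on food amounts, and the protocol does not show that the supplement meets that condition, most clearly for the 10 of 22 mg (45%) that is MZ. That conclusion rests on the protocol's own text and one division. The number of people affected is assumed to be very small. There is no effect on the analysis and no evidence of harm in the documents. It merits correction because it concerns participant protection and costs little, not because it is likely to arise often.

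**What to change.** Reconcile Selection of Subjects, the Inclusion and Exclusion criteria, and the Risks text, so that the entry criteria and the pregnancy and breast-feeding statement cover the same people. There are two routes, and the choice belongs to the sponsor and the IRB:

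1. State an entry criterion on pregnancy and breast-feeding, established by self-report.
2. Document a safety basis for this group at the supplement amounts, MZ included, and revise the Risks sentence to match.

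The first route acts only at entry and says nothing about pregnancy that begins during the study. The sponsor should make clear whether the safety statement is meant to extend to that situation.

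Separately, stop using the spinach comparison to support the MZ content. If it is kept for L and Z alone, rescale it to 12 mg, about 1.1 bowls on the protocol's own ratio.

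Cost: a line or two of protocol text and one wording change. The first route adds no test and loses at most a very few otherwise eligible patients (an assumption). The second loses none, but needs evidence that the protocol does not now contain. No dose is proposed.
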